11.4.2 Safety Population

Includes all trial subjects that:

- Provide consent; and
- Are randomized; and
- Receive at least one dose of the study treatment, and
- Provided any evaluable safety data.

The Safety Population will be used for all safety analyses and will be analysed as actually treated.

11.4.3 Immunogenicity Population up to Day 57

Includes all subjects in the Safety Population that:

- Have immunological results for Days 1, 15, 29, 36, 43, and 57 (subjects who withdraw early and do not complete all assessment days will still be included for analyses); and
- Did not experience a laboratory confirmed COVID-19 illness between Day 1 and Day 57; and
- Did not receive any prohibited medication during the study to Day 57 that is medically assessed to potentially impact the immune response (and immunogenicity results); and
- Have no major protocol deviations affecting the primary immunogenicity outcomes as determined by the Sponsor prior to database lock and unblinding.

The Immunogenicity Population will be the primary population used for immunogenicity analyses for the Day 57 analyses for each of Part 1 and Part 2.

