9.9 Sample Collection and Processing

Over the course of the study, a blood sample will be collected at each visit (total of no more than 36 blood samples from each subject) for screening, safety laboratory and immunological assessments. Sample volume collected will vary between 15 mL and a maximum of 73 mL with individual samples collected into multiple tubes to facilitate disparate immunological tests (see table below for details).

A total of 8 blood samples will be collected for safety laboratory assessments from each subject, one sample at screening, pre-dose (within 60 minutes pre-dose), and 1, 7, and 14 days post dose for each dose (Days 1, 2, 8, 29, 30, 36). Each sample will consist of 15 mL of whole blood.

PD samples collected for immunogenicity assessment will 4 mL for T-cell analysis, 10 mL for ELISA, Luminex assay, virus neutralisation assay, and ADCC analysis, and 20 mL for isolation and cryopreservation of PBMCs. Pre-dose samples should be taken within 60 minutes of dosing, but all other samples may be taken within the visit window specified in Section 9.2.

Sample collections performed outside the pre-defined time windows are protocol deviations, however will be used for immunological, safety and statistical analyses. Unless otherwise specified, or for subject safety, when blood draws and other procedures coincide, blood draws will have precedence. Blood samples will be collected by direct venipuncture.

The total volume of blood including that collected for eligibility screening and safety purposes should not exceed 500 mL for the whole study, with up to 400 mL collected at visits between Day 1 and Day 57±2, and up to 100 mL collected at the Day 209±5 and 394±5 visits. All blood samples will be collected and processed as per the supplementary study specific laboratory manuals.

Table 1: Summary of all blood samples collected over the study Part 1 (Cohorts 1-3)

Visit	Total Collection Volume (mL)	Number of Samples Collected and Purpose of Sample			
		Safety Lab (15 mL)	PD (3-4 ml Whole blood)	PD (8-10 mL Serum)	PD 10-20 mL PBMCs)
Screening	29	1	1	1	0
Day 1 (first dose)	63	1	2	2	1
Day 2	15	1	0	0	0
Day 8	39	1	1	0	1
Day 15	34	0	1	1	1
Day 29 (second dose)	49	1	1	1	1
Day 30	15	1	0	0	0
Day 36	43	1	2	0	1
Day 43	34	0	1	1	1
Day 57	59	1	1	2	1
Day 120	10	0	0	1	0
Day 209	40	0	0	2	1
Day 394	20	0	0	2	0
Total volume	450				

Table 2: Summary of all blood samples collected over the study Part 2 (Cohorts 4-6)

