Visit	Total Collection Volume (mL)	Number of Samples Collected and Purpose of Sample			
		Safety Lab (15 mL)	PD (3-4 ml Whole blood)	PD (8-10 mL Serum)	PD 10-20 mL PBMCs)
Screening	25	1	0	1	0
Day 1 (first dose)	63	1	2	2	1
Day 2	15	1	0	0	0
Day 8	39	1	1	0	1
Day 15	34	0	1	1	1
Day 29 (second dose)	45	1	0	1	1
Day 30	15	1	0	0	0
Day 36	39	1	1	0	1
Day 43	34	0	1	1	1
Day 57	55	1	0	2	1
Day 209	30	0	0	1	1
Day 394	10	0	0	1	0
Total volume	404				

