9.18 Premature Termination of the Study

The study may be prematurely terminated by the Investigator following consultation with the Sponsor, by the Sponsor or by the regulatory authorities. Following a decision to discontinue the trial, the Investigator will promptly inform the active study subjects and the HREC responsible for this trial, stating the reasons for discontinuation of the study and, furthermore, advise them in writing of any potential risks to the health of study subjects or other persons. It is the Sponsor's responsibility to report the premature termination of the study to the regulatory authority(ies), when required by the applicable regulatory requirement(s).

10. Analytical Methodology

When applicable, samples will be transported to the bioanalytical facilities in at least two separate shipments, with each set of aliquots in separate shipments. Once the bioanalytical laboratory confirms receipt of the first shipment, the second set of aliquots may be sent. The samples should be packed on sufficient dry ice to keep them frozen for at least 72 hours.

Tetra-Q will analyse SARS-CoV-2 specific antigen in serum samples using a validated method.

The Peter Doherty Institute for Infection and Immunity will analyse live virus neutralisation in serum samples using a validated method.

The University of Queensland will perform T-cell analysis via multi-colour cell cytometry which will include assessment of markers of a Th2 immune response (CD3, CD4, CD8, TFN- γ , TNF- α , IL-2, IL-4, IL-13, IL-17a, CD107a, and Granzyme B) in whole blood samples and cryopreserved peripheral blood mononuclear cells (PBMCs) using a validated method.

The bioanalytical work in support of the study will be conducted in compliance with the GCP, using the SOPs in place each respective laboratory. These SOPs are in accordance with applicable regulations in the industry: Guidelines on Bioanalytical Method Validation, Good Laboratory Practice (GLP), and Guideline for GCP ICH E6 (R2).

Samples from subjects included in the Safety Population (see Section 11.4.3) and from subjects who were withdrawn from the study due to adverse events will be analysed.

11. Statistical Analyses

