11.5 Immunogenicity Analysis

For the evaluation of immunogenicity, vaccine antibody titres will be analysed using the Immunogenicity Population and the methodology described previously in Section 11:

- Geometric Mean Titres (GMT) on Days 1, 15, 29, 43 and 57, and 209 and 394 will be summarized using descriptive statistics by treatment group compared to placebo;
- Seroconversion on Days 15, 29, 43, 57, 209 and 394, compared to placebo. Seroconversion is defined as the percentage of subjects with a ≥ 4 fold increase in post-vaccination titre compared to Day 1;
- Geometric Mean Fold increases on Day 15 / Day 1, Day 29 / Day 1, Day 43 / Day 1, and Day 57 / Day 1, Day 209 / Day 1, and Day 394 / Day 1, compared to placebo;
- Fold increase in antigen specific CD4+ T-cells at Days 8, 15, 29, 36, 43, and 57 compared to Day 1 for vaccine antigen dose versus placebo;
- Fold increase in antigen specific CD8+ T-cells at Days 8, 15, 29, 36, 43, and 57 compared to Day 1 for vaccine antigen dose versus placebo;
- Fold increase in antibody dependent cellular cytotoxicity (ADCC) at Days 15, 29, 43, 57, 209, and 394 compared to Day 1 for vaccine antigen dose versus placebo;
- Fold increase in antibodies elicited to the Receptor Binding Domain (RBD), N-Terminal Domain (NTD), and clamp trimerization domain on Days 15, 29, 43, 57, 209, and 394 compared to Day 1 for vaccine antigen dose versus placebo; and
- Fold increase in antigen specific humoral immune responses including isotypes IgM, IgA, IgE, and subtypes IgG1, IgG2, IgG3 and IgG4 at Days 15, 29, 43, 57, 209, and 394 compared to Day 1 for vaccine antigen dose compared to placebo.

Once all subjects have completed Day 57, an interim analysis will be performed. The immunogenicity analysis will be included as part of this interim analysis.

12. Final Report

A final report including clinical, bioanalytical, and statistical sections will be the responsibility of Delve Medical Writing and will be signed and approved by at least the Sponsor.

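### The primary immunogenicity population requires a Day 36 result, although no serum is drawn and no titre is analysed on that day

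*Protocol*

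**What the plan says.** Section 11.4.3 builds the Immunogenicity Population up to Day 57 from the Safety Population with four conditions joined by 'and'. The first is that subjects "Have immunological results for Days 1, 15, 29, 36, 43, and 57 (subjects who withdraw early and do not complete all assessment days". The rest of the bracket exempts those who drop out, saying that they "will still be included for analyses". Early withdrawal is the only exemption named. The section makes this the primary population for the Day 57 immunogenicity analyses in each Part, and Section 11.4.4 takes the Full Immunogenicity Population from it.

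The titre schedule is different. Section 11.5 summarises "Geometric Mean Titres (GMT) on Days 1, 15, 29, 43 and 57", then Days 209 and 394. The primary endpoints in Section 5.4 are the ELISA and microneutralisation GMTs at Days 29 and 57. In Section 9.9, Tables 1 and 2 list no serum tube on Day 36 in either Part.

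Day 36 appears among the T-cell analyses. Section 5.4 has exploratory CD4+ and CD8+ endpoints at Days 15, 29, 36, 43 and 57. Section 11.5 adds a further day: "Fold increase in antigen specific CD4+ T-cells at Days 8, 15, 29, 36, 43, and 57 compared to Day 1". Section 10 says the T-cell work is done "in whole blood samples and cryopreserved peripheral blood mononuclear cells (PBMCs) using a validated method".

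**The concern.** A population for titre analyses should depend on what those analyses need. Here entry also depends on a visit that cannot produce a titre. A missed Day 36 visit, or failure of both cell materials, would remove a subject's valid Day 29 and Day 57 titres from the primary GMTs, the GMT ratios and the seroconversion summaries.

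The exemption makes the rule uneven. A subject who drops out and misses several listed days is kept; a subject who stays and misses one is not. The same wording applies to Days 15 and 43. Those days do carry secondary titre endpoints, so requiring them is easier to defend, but neither is needed for a Day 29 or Day 57 GMT.

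What is at stake is precision and consistency in the data that inform dose selection, with 24 subjects per active group and 8 placebo subjects per cohort.

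**Working it through.** **1. Is the zero serum count on Day 36 real, or a broken table row?** Section 9.9 gives 15 mL per safety sample, 4 mL whole blood for T-cells, 10 mL serum (ELISA, Luminex, neutralisation, ADCC) and 20 mL for PBMCs. So volume = 15 × safety + 4 × whole blood + 10 × serum + 20 × PBMC.

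- Table 1, Day 36: 15 + 2×4 + 0 + 20 = 43 mL, as stated.
- Table 2, Day 36: 15 + 4 + 0 + 20 = 39 mL, as stated.

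One serum tube would give 53 and 49 mL. Every other row fits the same formula, and the rows add up to the stated totals of 450 and 404 mL. The zero is real.

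**2. Day lists up to Day 57**

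| Use | Days |
|---|---|
| Entry condition (11.4.3) | 1, 15, 29, 36, 43, 57 |
| Titre analyses (11.5) | 1, 15, 29, 43, 57 |
| Primary titre endpoints (5.4) | 29, 57 |
| T-cell endpoints (5.4), against pre-vaccination | 15, 29, 36, 43, 57 |
| T-cell analyses (11.5), against Day 1 | 8, 15, 29, 36, 43, 57 |

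Day 36 is the only entry day without a titre.

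**3. When does the condition fail?** Whole blood or PBMCs can each supply the Day 36 result, and for late or early draws Section 9.9 says: "Sample collections performed outside the pre-defined time windows are protocol deviations, however will be used for immunological, safety and statistical analyses". The condition therefore fails if the visit is missed (rate m) or both materials fail (rate f each, taken as independent): m + (1−m)f². With an assumed f of 10%, both fail at 1% of attended visits, and m = 1%, 2%, 5% gives 2.0%, 3.0%, 5.9%. The missed-visit rate accounts for most of this at the higher values of m.

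**4. Size of the Day 36 condition alone.** The protocol gives no missing-data rate, so the rates below are assumptions. Each listed day lacks any result with probability 1%, 2%, 5% or 10% in subjects who do not withdraw; 10% is a pessimistic end. The loss due to Day 36 alone is q = P(other five days present) − P(all six present). The standard-error ratio is √(five-day ÷ six-day probability). The chance that at least one of the 120 Part 1 subjects is lost is 1 − (1−q)^120, treating all 120 as staying in the study.

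*Independent across visits*, P(k days present) = (1−rate)^k:

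| Rate | Five days | Six days | q | of 24 | of 120 (Part 1) | of 96 (Part 2) | SE ratio | P(≥1 of 120) |
|---|---|---|---|---|---|---|---|---|
| 1% | 0.951 | 0.941 | 0.0095 | 0.23 | 1.14 | 0.91 | 1.005 | 0.68 |
| 2% | 0.904 | 0.886 | 0.0181 | 0.43 | 2.17 | 1.74 | 1.010 | 0.89 |
| 5% | 0.774 | 0.735 | 0.0387 | 0.93 | 4.64 | 3.71 | 1.026 | 0.99 |
| 10% | 0.590 | 0.531 | 0.0590 | 1.42 | 7.09 | 5.67 | 1.054 | 0.999 |

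*Clustered within subjects*, beta-binomial with assumed intraclass correlation 0.3. With a = (1−rate)×0.7/0.3 and b = rate×0.7/0.3, P(k days present) is the product of (a+j)/(a+b+j) for j = 0 to k−1:

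| Rate | q | of 24 | SE ratio | P(≥1 of 120) |
|---|---|---|---|---|
| 1% | 0.0031 | 0.07 | 1.002 | 0.31 |
| 2% | 0.0060 | 0.14 | 1.003 | 0.51 |
| 5% | 0.0136 | 0.33 | 1.008 | 0.81 |
| 10% | 0.0232 | 0.56 | 1.016 | 0.94 |

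**5. Size of the whole six-day condition.** A Day 57 GMT adjusted for baseline needs only Days 1 and 57. Under independence the six-day rule costs (1−rate)² − (1−rate)⁶ of subjects: at 2%, 0.9604 − 0.8858 = 0.0746, or 1.8 of 24; at 5%, 0.9025 − 0.7351 = 0.1674, or 4.0 of 24. Step 4 therefore understates what replacing the whole condition would recover.

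**The case against.** The strongest reply is that Day 36 is not a stray entry. The list is Day 1 plus exactly the T-cell endpoint days in Section 5.4, and one population serves all the immunogenicity analyses. Day 8 appears only in the Section 11.5 analysis list, so its absence from the entry condition proves little about the T-cell endpoints. That explains where Day 36 came from. It does not give a reason to make titres depend on it, and the Section 11.5 analyses at Day 8 show that T-cells can be analysed on a day that is not a condition of entry.

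Second, the bracketed exemption may be loose drafting meant to cover any incomplete subject, and Section 11 lets the SAP supersede the protocol. This is possible, but the text names only subjects who withdraw. If everyone was meant, the six-day condition does nothing. Either way the sentence needs correcting.

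Third, the effect is small and the rates are assumed. This stands. One subject lost out of 120 is immaterial, so the chance of at least one exclusion shows only that the rule would probably be invoked, not that it would do much harm.

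Fourth, a narrower correction would do: remove Day 36 for titres, or extend the exemption to any missed visit. The first would leave the same problem at Days 15 and 43. The second would leave a condition that excludes nobody.

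**Conclusion.** The concern holds. As written, the primary population can exclude a subject's valid primary titres for want of an exploratory result, while keeping subjects who drop out. This should be fixed, but the effect is minor to moderate.

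Under the assumed 1% to 10% rates, the Day 36 condition costs each arm of 24 at most about 1.4 subjects and 5.4% in standard error; if misses cluster, at most about 0.6 subjects and 1.6%. These figures rest on the assumed rates, the assumed correlation and the literal reading of the exemption.

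No bias has been shown. No decision threshold moves, because Section 8.2 has no power calculation and Section 11.3 no success rule. The carry-over to Section 11.4.4 adds little, since that set is already limited to subjects who complete Days 209 and 394.

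**What to change.** Replace the six-day condition in Section 11.4.3 with: *has a Day 1 result and at least one post-dose result for the assay being analysed*. Keep the other three conditions. Analyse each endpoint at each visit in all such subjects who have that visit's result, whether or not they withdraw or miss other visits, and show n by visit and assay. Day 36 results then bear only on the T-cell analyses, and a subject with T-cell results but no titre stays in those. State that Section 11.4.4 inherits the corrected set assay by assay, so that it is clear which set is meant.

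This is a change of wording, with no new samples or visits. The cost is that denominators differ slightly between visits and assays, so there is no single common set. Keeping early withdrawals already has that effect under the present text.

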5.4 Study Endpoints

Primary Safety Endpoints:

- Frequency, duration, and intensity of solicited local adverse events (AEs), including pain, redness, and induration for 7 days following each study treatment (for Days 1-3, Days 4-7 and Days 1-7).
- Frequency, duration, and intensity of solicited systemic adverse events (AEs), including fever, nausea, chills, diarrhoea, headache, fatigue, and myalgia for 7 days following each study treatment (for Days 1-3, Days 4-7 and Days 1-7).
- Frequency, duration, intensity, duration, and relatedness of unsolicited AEs through to Day 57. Frequency of Serious Adverse Events (SAEs), Medically-Attended Adverse Events (MAAEs), and any AEs leading to study withdrawal (including decision by the Principal

Investigator (PI) not to proceed with the second dose) at any time during study through to Day 394. Frequency and intensity of unsolicited AEs through to Days 57, 209, and 394

Primary Immunogenicity Endpoints:

- Geometric mean titre (GMT) of the serum antibody response to the Sclamp antigen compared to placebo by antigen specific ELISA at Day 29 (28 days after first dose) and Day 57 (28 days after second dose).
- GMT of the serum NAb titres to SARS-CoV-2 virus compared to placebo by MN assay at Day 29 (28 days after first dose) and Day 57 (28 days after second dose).

Secondary Immunogenicity Endpoints:

- Proportion of subjects with ≥ 4 fold increase in titre above baseline by ELISA at Days 15, 29, 43, 57, 209, and 394 post-first study treatment administration compared to placebo.
- Proportion of subjects with ≥ 4 fold increase in titre above baseline by MN assay at Days 15, 29, 43, 57, 209, and 394 post-first study treatment administration compared to placebo.
- GMT of the serum antibody response to the Sclamp antigen compared to placebo by antigen specific ELISA at Days 1, 15, 29 (28 days after first dose), and Days 43, 57 (28 days after second dose) and Days 209 and 394 (6 and 12 months post-second dose respectively).
- GMT of the serum NAb titres to SARS-CoV-2 virus compared to by MN assay at Days 1, 15, 29 (28 days after first dose), and Days 43, 57 (28 days after second dose) and Days 209, 394.

Exploratory Immunogenicity Endpoints:

- Proportion of subjects experiencing laboratory confirmed SARS-CoV-2 infection and/or severity graded COVID-19 disease between Days 57 and 394 compared to placebo.

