11.4.4 Full Immunogenicity Population

Includes all subjects in the Immunogenicity Population that:

- Have also completed follow-up examinations on Days 209 and 394; and
- Did not experience a laboratory confirmed COVID-19 illness between Day 1 and Day 394.

The Full Immunogenicity Population will be the primary population used for follow-up analyses.

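### Any confirmed COVID-19 illness removes a subject's titres at every visit, including those drawn before infection; the loss is probably small, but a sample-level rule would avoid it

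*Protocol*

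**What the plan says.** Section 11.4.3 builds the Immunogenicity Population from subjects, not samples: "Includes all subjects in the Safety Population that" meet a list of conditions, one of which is "Did not experience a laboratory confirmed COVID-19 illness between Day 1 and Day 57". Its role is fixed in the same section: "The Immunogenicity Population will be the primary population used for immunogenicity analyses for the Day 57 analyses". That section also keeps partial data in another situation: "subjects who withdraw early and do not complete all assessment days will still be included for analyses".

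Section 11.4.4 narrows this set to subjects who completed both the Day 209 and Day 394 examinations and who meet a longer condition, "Did not experience a laboratory confirmed COVID-19 illness between Day 1 and Day 394". Its role is also fixed: "The Full Immunogenicity Population will be the primary population used for follow-up analyses". Section 11.5, however, lists GMTs, seroconversion and fold rises at Days 209 and 394 under the Immunogenicity Population.

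The primary immunogenicity endpoints in 5.4 are ELISA and microneutralisation GMTs at Days 29 and 57. Section 5.4 also has an exploratory endpoint: "Proportion of subjects experiencing laboratory confirmed SARS-CoV-2 infection and/or severity graded COVID-19 disease between Days 57 and 394 compared to placebo". Sections 11 and 12 plan one addendum after the Day 209 visit and another after the Day 394 visit. Section 11.4.1 assigns the ITT Population only to listings and demographic summaries. Nothing in the protocol keeps titres drawn before an infection.

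**The concern.** An infection contaminates only the titres drawn after it. Setting those aside is sound, because they mix the response to vaccine with the response to virus. Removing the earlier titres has no such reason behind it.

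Two things are at stake. The first is lost data in a small trial: one subject is 1/24 = 4.2% of an active arm, or 1/8 = 12.5% of one cohort's placebo group. The second is selection. By comparing infection with placebo, the protocol treats it as an outcome that vaccination may affect. If low responders in a vaccine arm are infected more often, dropping their clean early titres raises that arm's GMT. Section 11.3 bases the choice of dose and regimen on the joint safety and immunogenicity profiles, so these estimates matter even without hypothesis tests.

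There is also a practical problem. Membership of the follow-up set depends on events up to Day 394, but the set is named primary for follow-up analyses that include a report written after Day 209.

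**Working it through.** **Inputs from the protocol.** The cohort sizes in 8.2 reproduce the planned total: 32 + 32 + 56 + 32 + 32 + 32 = 216, with 24 subjects per active group and 8 placebo subjects per cohort. No power calculation, titre SD or COVID-19 rate is given.

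**Clean titres removed, by infection date**

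| Infection falls on | Post-dose titres drawn before infection but removed | Set |
|---|---|---|
| Days 30-57 | Day 15 and Day 29, and Day 43 if infected later than that | 11.4.3 |
| After Day 209 | Day 209 | 11.4.4 |

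An infection after Day 57 does not touch the Day 29 and Day 57 primary analyses.

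**Expected loss per 24-subject arm.** Assume a cumulative risk r by Day 394, with r from 0 to 10%, and a constant hazard over the 393 days from Day 1. The proportion still uninfected d days after Day 1 is (1 - r)^(d/393). At r = 10%:
- All exclusions to Day 394: 24 x 0.10 = 2.4.
- Infected after Day 209: 24 x (0.9^(208/393) - 0.9) = 24 x (0.9458 - 0.9000) = 1.10.
- Infected by Day 57: 24 x (1 - 0.9^(56/393)) = 24 x 0.0149 = 0.36.
- Infected between Day 29 and Day 57: 24 x (0.9^(28/393) - 0.9^(56/393)) = 24 x (0.9925 - 0.9851) = 0.18.

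Spreading infections evenly over time gives nearly the same answers: 2.4 x 185/393 = 1.13 and 2.4 x 28/393 = 0.17. At r = 0 every figure is 0.

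**Precision.** For a GMT ratio of 24 versus 24 with an assumed log10 SD of 0.5, the 95% CI multiplies and divides by 10^(t x 0.5 x sqrt(1/24 + 1/24)) = 1.95. With one arm at 23 it is 1.97, and at 22 it is 1.98. Loss of precision is therefore slight.

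**Selection.** A simulation let the odds of infection fall by a factor of exp(0.5) to exp(1.0) per SD of titre, with log10 SD from 0.3 to 0.7. All of these are assumptions. Dropping infected subjects raised the arm's GMT by 0.4-1.8% when 1% were dropped, 1.8-8.1% at 5% and 3.5-15.9% at 10%. At r = 10% the share of an arm wrongly dropped is 0.18/24 = 0.7% for Day 29, which lies below the 1% row. For Day 209 it is 1.10/24 = 4.6%, close to the 5% row.

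**Timing.** The Day 209 addendum covers data up to that visit. Whether a subject stays COVID-free to Day 394 is settled about 185 days later, so the 11.4.4 condition cannot be evaluated in time for that report.

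**The case against.** Leaving infected subjects out of an immunogenicity set is a conventional per-protocol choice, and it avoids having to date infections when scheduled swabs are sparse. The trial has no hypotheses, power calculation or success rule, so no error rate is affected. The SAP, not seen here, supersedes the protocol where they differ. All of this limits the consequences. None of it gives a reason to drop titres drawn before infection, and the rule is explicit protocol text, not a detail left open.

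Several stronger readings are tempting, and the document does not support them:
- *All 2.4 exclusions per arm at a 10% rate are valid Day 209 titres lost.* Infections before Day 209 would be set aside at Day 209 under any sensible rule; only about 1.1 are wrongly lost.
- *A late infection removes the Day 209 titre from every analysis.* Section 11.5 places Day 209 and Day 394 analyses under the Immunogenicity Population, which looks only to Day 57 and keeps that titre. The conflict is with 11.4.4, which names the other set primary for follow-up.
- *Both sets already tolerate a varying n.* That is true of 11.4.3, through its early-withdrawal clause. The 11.4.4 set requires completion of both follow-up visits.
- *The placebo GMT is distorted.* Baseline titres are expected at or below LLOQ and imputed as half of it (sections 11 and 11.2). Uninfected placebo titres should stay near that level, so dropping some moves the placebo GMT very little.

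**Conclusion.** The point holds as a minor one. As written, the two definitions discard valid pre-infection titres, including Day 29 primary titres, and condition on a post-randomisation outcome. The follow-up condition also cannot be applied when the Day 209 addendum is written, and 11.4.4 and 11.5 disagree about which set the follow-up analyses use.

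The size rests on an assumed 0-10% infection rate by Day 394 with constant hazard: about 0-0.2 valid Day 29 titres and 0-1.1 valid Day 209 titres lost per 24-subject arm. A reader might infer that the vaccine GMTs will be materially inflated. The protocol does not support that: it supplies neither an infection rate nor a titre-risk gradient. Even with the assumed gradients, the Day 29 effect at the top of the range stays below about 2%, against a CI factor near 1.95. The long follow-up is more exposed, mainly in the vaccine arms, and a highly effective vaccine would leave fewer infections there to exclude.

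**What to change.** In 11.4.3 and 11.4.4, replace the subject-level COVID-19 condition with a sample-level one. For subjects with laboratory confirmed (RT-PCR) COVID-19 illness, set aside titres drawn on or after the earlier of symptom onset or the first RT-PCR-positive swab, and analyse earlier titres. The trigger should not be any positive SARS-CoV-2 test: section 9.10.6.7 includes serum antibody ELISA in that test at screening, and vaccination can turn serology positive. State in 11.4.4 and 11.5 which set is used at Days 209 and 394.

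The separate requirement in 11.4.4 to have completed both follow-up visits has the same timing problem for the Day 209 addendum. It needs its own decision, because the sample-level rule does not remove it.

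The cost is about one sentence per definition plus the alignment with 11.5. The number of subjects will vary by visit, which is new for the Full Immunogenicity Population, and infection onset will be dated with some uncertainty.
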